9.3.8 Investigational Product Accountability

The study site staff is responsible for maintaining accurate records (including dates and quantities) of IP(s) received, patients to whom IP is dispensed (patient-by-patient dose specific accounting), IP returned, and IP lost or destroyed. The Investigator and the study site staff must retain all unused or expired study supplies until the study monitor (on-site CRA) has confirmed the accountability data.

9.3.9 Return and Disposition of Clinical Supplies

Unused IP must be kept in a secure location for accountability and reconciliation by the study monitor. The Investigator or designee must provide an explanation for any destroyed or missing IP or study materials.

Unused IP may be destroyed on site, per the site's standard operating procedures, but only after Catalyst has granted approval for drug destruction. The monitor must account for all IP in a formal reconciliation process prior to IP destruction. All IP destroyed on site must be documented. Documentation must be provided to Catalyst and retained in the Investigator study files. If the site is unable to destroy IP appropriately, the site can return unused IP to Catalyst upon request. The return of IP or IP materials must be accounted for on a Study Drug Return Form provided by Catalyst.

All IP and related materials should be stored, inventoried, reconciled, and destroyed or returned according to applicable regulations and study procedures.

9.4 Prior and Concomitant Medications

All prescription and over-the-counter medications and herbal and nutritional supplements taken by a patient for 14 days before the Screening visit will be recorded on the designated CRF. Additionally, the stop date of any medications the patient was taking within 6 months before Screening that are excluded or restricted by the protocol will be recorded.

The Investigator may prescribe additional medications during the study, if the prescribed medication is not prohibited by the protocol. In the event of an emergency, any needed medications may be prescribed without prior approval, but the medical monitor must be notified of the use of any contraindicated medications immediately thereafter. Any concomitant medications added or discontinued during the study should be recorded on the CRF.

Medications that are contraindicated when combined with amifampridine phosphate are:

- Medicinal products with narrow therapeutic window
- Sultopride

Amifampridine phosphate should be used with caution when combined with the following products:

Medicinal products known to lower the epileptic threshold

- Medicinal products with atropinic effects
- Medicinal products with cholinergic effects
- Non depolarizing muscle relaxant acting medicinal products
- Depolarizing muscle relaxant acting medicinal products.

Medications prohibited during the study are listed in Table 3.

Table 3. Medications Prohibited During Study

Nusinersen must be stopped at least 6 months before screening. Salbutamol, is permitted only if the dose has been stable for 6 months before screening.

Any investigational product (other than amifampridine) or an investigational medical device within 6 months before Screening.

Medications that are contraindicated when combined with amifampridine phosphate are:

- Medicinal products with narrow therapeutic window
- Sultopride

Amifampridine phosphate should be used with caution when combined with the following products:

- Medicinal products known to lower the epileptic threshold
- Medicinal products with atropinic effects
- Medicinal products with cholinergic effects
- Non depolarizing muscle relaxant acting medicinal products
- Depolarizing muscle relaxant acting medicinal products.

9.5 Dietary or Other Protocol Restrictions

9.5.1 Dietary Restrictions

There are no dietary restrictions for patients during any part of this study.

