A Phase 1 open-label, randomized, single-dose, 2-treatment, 2-period crossover study in 46 healthy volunteers evaluated whether food consumption significantly affected the bioavailability of amifampridine phosphate tablets (LMS-001). Each subject received 20 mg amifampridine phosphate on 2 occasions, once fasting and once after consumption of a standard high fat breakfast. Each single 20 mg dose of amifampridine phosphate were administered 6 days apart. The results from this study indicate co-administration with food reduces exposures determined by C_{max} and AUC by approximately 40% and 20%, respectively. In addition, the time to maximum serum concentrations (T_{max}) was increased 2fold from approximately 38 minutes (fasted) to 78 minutes (fed). The drug was well tolerated with no serious adverse events and only 1 severe event, an episode of gastroenteritis unrelated to amifampridine. The most common AEs occurring in $\geq 10\%$ of subjects were: oral paresthesia (20 subjects; 43%), peripheral paresthesias (12; 26%), dizziness (5; 11%), headache (5; 11%), and oral hypoesthesia (5; 11%). Abdominal pain, nausea, peripheral paresthesias, dizziness, and headache were more commonly reported by subjects following administration of amifampridine phosphate in the fasted state. In humans, amifampridine is exclusively metabolized to a single major metabolite, 3-N-acetyl amifampridine, via N-acetyl transferases (NAT) (Catalyst internal in vitro and in vivo studies; data available upon request). There are 2 NAT enzymes, NAT1 and NAT2, both of which are principally hepatic and both of which are highly polymorphic. These allelic variations lead to slow and fast metabolic rates, which have been well characterized in the Caucasian and Asian populations, but somewhat less well in African populations (Sabbagh, 2006). Slow acetylators are estimated to comprise 50% to 59% of the Caucasian population, with the remainder being rapid acetylators (fast + intermediate). Fast acetylators are over represented in Asian population (92% of Japanese and 80% of Chinese) while they may be under represented in

African populations (25%) (Cascorbi, 1995). Slow acetylators will accumulate drug to higher levels (i.e. higher C_{max}) and clear drug more slowly (i.e. longer $t_{1/2}$), both of which may increase the risk of drug related toxicity (Fukino, 2008; Jetter, 2009).

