9.3.3 Directions for Administration

All doses of study treatment will be taken at home, except one of the doses on the day of the in-clinic study visits, when it will be administered by study personnel and will be administered in the clinic to facilitate timing of efficacy assessments. Test medication should be taken every day at approximately the same time, at the dose and frequency instructed by Investigator. On the day of an in-clinic study visit (Days 0, 7, 14, 21, and 28), dose administration will be the medication the patient has been taking for the previous days, but administered by the study personnel 45 minutes before the first efficacy assessment. If the patient takes the dose three times a day, the patient should be given specific instructions on dosing relative to the time of their visit to assure a dose will be given during the in-clinic visit within the required time window. All safety assessments will be performed before the dose is administered to the patient during the in-clinic visit. Efficacy assessment will be performed at standardized times relative to the dose administered in the clinic.

Assessment	Start Time After Dose (+ 10 minutes unless otherwise specified)
HFSME	45 minutes
6-minute walk test	After HFSME
Time to rise from floor	After 6-minute walk
Time to rise from chair	After rise from floor
Time to climb 4 stairs	After rise from chair
Time to walk 10 meters	After climb stairs
Quality of Life Assessment	After 10-meter walk

The dose of amifampridine will be individually determined by the Investigator, within the bounds of a total daily dose of 15 mg to 80 mg, divided into doses taken 3 to 4 times per day as prescribed by the Investigator, based on optimal neuromuscular benefit. The maximum single dose is 20 mg. Amifampridine dose will be titrated upward every 3 to 4 days, starting at 15 mg/day, at the discretion of the Investigator. Pediatric dosing guidelines are presented in Table 2.

Table 2 Pediatric Dosing Guidelines

	Ages 6 to 16 Years	Ages >16 years
Recommended starting dose	5 mg, 3 times per day (15 mg/day total)	10 mg, 3 times per day (30 mg/ day total)
Initial dose escalation	May increase dose to 10 mg, 3 times per day (30 mg/day total)	May increase dose to 10 mg, 4 times per day (40 mg/day total)

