12.3.2 Period 1, Days 7 and 14 (or Early Termination Visit)

Patients will report to the study site on Days 7 and 14 (±1 day) and have the assessments/procedures listed below completed. Study personnel will administer a dose of the patient's blinded medication at the clinic on Days 7 and 14, so assessments can be performed according to the specified times in relation to the time of dose administration. The medication administered by study personnel should be the same as what the patient has been taking for Period 1. If the patient is taking study medication 3 or 4 times a day, the visit needs to be arranged such that one of the doses is administered by the study site personnel, and assessments should occur after the same dose each visit.

- Assessment of AEs/SAEs;
- Vital signs (seated position), including SBP, DBP, heart rate, respiration, and body temperature;
- Urine pregnancy test in females of childbearing potential (only on Day 14);
- Concomitant medications;
- Collect patient Drug Dosing Diary and perform IP accountability (a new Drug Dosing Diary is given to the patient on Days 7 and 14);
- Efficacy assessments following in-clinic dose of double-blind medication as listed below:

Order of Assessment at Each Study Visit (when applicable)	Start Time After Dose (+ 10 minutes unless otherwise specified)
HFSME	45 minutes
6-minute walk test	After HFSME
Time to rise from floor	After 6-minute walk
Time to rise from chair	After rise from floor
Time to climb 4 stairs	After rise from chair
Time to walk 10 meters	After climb stairs
Quality of Life Assessment	After 10-meters walk

• INQoL for neuromuscular disease or the PEDSQLTM assessments will be completed for adult or pediatric patients, respectively after the six other assessments have been made.

On Day 14, all Period 1 study medication should be collected after the assessments have been performed, and study medication for Period 2 dispensed. The first dose of Period 2 medication is to be administered after the assessments are completed and at the time of the next regularly scheduled dose.

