12.4 Period 2, Days 21 and 28 (or Early Termination Visit)

Patients will report to the study site on Days 21 and 28 (± 1 day) and have the assessments/procedures listed below completed. Study personnel will administer a dose of the patient's blinded medication at the clinic on Days 21 and 28, so assessments can be

performed according to the specified times in relation to the time of dose administration. The medication administered by study personnel should be the same as what the patient has been taking for Period 2. If the patient is taking study medication 3 or 4 times a day, the visit needs to be arranged such that one of the doses is administered by the study site personnel.

- Assessment of AEs/SAEs;
- Complete physical exam (Day 28 only);
- Vital signs (seated position), including SBP, DBP, heart rate, respiration, and body temperature;
- 12-lead ECG (Day 28 only);
- Clinical laboratory tests (Day 28 only);
- Urine pregnancy test in females of childbearing potential (Day 28 only);
- Concomitant medications;
- Collect patient Drug Dosing Diary and perform IP accountability (a new Drug Dosing Diary is given to the patient on Day 21);
- Efficacy assessments following in-clinic dose of double-blind medication as listed below:

Order of Assessment at Each Study Visit (when applicable)	Start Time After Dose (+ 10 minutes unless otherwise specified)
HFSME	45 minutes
6-minute walk test	After HFSME
Time to rise from floor	After 6-minute walk
Time to rise from chair	After rise from floor
Time to climb 4 stairs	After rise from chair
Time to walk 10 meters	After climb stairs
Quality of Life Assessment	After 10-meters walk

• INQoL for neuromuscular disease or the PEDSQLTM assessments will be completed for adult or pediatric patients, respectively after the six other assessments have been made.

Page 53

On Day 28, all Period 2 study medication should be collected after the assessments have been performed. This represents the end of the study.

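### Efficacy tests are timed to 45 minutes after the clinic dose, but meal state is neither held constant within a patient nor recorded, and the same-dose rule is missing from Day 0 and Period 2

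*Protocol*

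**What the plan says.** **Timing.** On Days 0, 7, 14, 21 and 28 one dose is "administered by the study personnel 45 minutes before the first efficacy assessment" (Protocol 9.3.3). The HFMSE comes first, and its start may run late by up to "10 minutes unless otherwise specified", so it begins 45 to 55 minutes after the dose. The 6-minute walk, timed items and quality-of-life questionnaire follow in order (9.3.3, 9.7).

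**Food.** Section 9.5.1 says "There are no dietary restrictions for patients during any part of this study". Neither Table 1 nor the SAP's schedule (Appendix 1) lists meal time, fed state or a drug-level sample.

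**Food effect.** In study LMS-001 (7.4.1), 46 healthy volunteers took 20 mg "once fasting and once after consumption of a standard high fat breakfast". Food reduced Cmax and AUC "by approximately 40% and 20%, respectively", and Tmax went from about 38 to 78 minutes.

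**Same dose of the day.** The Days 7 and 14 text (12.3.2) adds that "assessments should occur after the same dose each visit". The matching paragraph for Days 21 and 28 (12.4) ends with "the visit needs to be arranged such that one of the doses is administered by the study site personnel", without that clause. The Day 0 text (12.3.1) lacks it too.

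**The concern.** A fixed clock after a supervised dose is meant to make drug exposure at the test similar from visit to visit. Meal state undoes part of that, because the sponsor's own data show that food lowers and delays the peak. The trial rests on within-patient differences in about 12 randomized patients, with no power calculation, so avoidable within-patient variation is costly.

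Day 0 is tested on open-label drug. It is the baseline for every change score, and it is the visit at which the 3-point HFMSE gain is judged. A patient could pass or miss that threshold partly on what was eaten beforehand. None of this can be repaired at analysis: no meal time is scheduled for recording, and the SAP 10.11 model has no term for it.

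The same-dose gap matters for a related reason. The treatment contrast in each patient is Period 1 against Period 2, and the rule is written only for Period 1.

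**Working it through.** **1. The plan's own figure.** 78 / 38 = 2.05, which reproduces the stated two-fold rise in Tmax.

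**2. Inputs, all from Protocol 7.4.1 and 9.3.3.** Tmax 38 min fasted and 78 min fed; AUC fed/fasted 0.80; Cmax fed/fasted 0.60, held back as a check; half-life 1.8 h (phosphate) or 1.6 h (base); test at 45 to 55 min.

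**3. Model.** The documents give no concentration at 45 minutes, so one is inferred from a one-compartment model with first-order absorption:

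C(t) = F × ka / (ka − ke) × [exp(−ke·t) − exp(−ka·t)]

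- ke = ln 2 / 1.8 = 0.385 per hour.
- ka is solved from ln(ka/ke) / (ka − ke) = Tmax: 4.13 per hour fasted, 1.35 per hour fed.
- F = 1 fasted, 0.80 fed.

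**4. Level at 45 minutes (0.75 h).**

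- Fasted: 1.103 × (0.749 − 0.045) = 0.776
- Fed: 0.80 × 1.399 × (0.749 − 0.363) = 0.432
- Fasted/fed: 0.776 / 0.432 = 1.80

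At 55 minutes the same steps give 0.750 / 0.462 = 1.62.

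**5. Check.** The model's fed/fasted Cmax is 0.62 (0.60 with the 1.6 h half-life), against 0.60 reported, although Cmax was not fitted.

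**6. Where the gap comes from.** At 45 minutes the fasted curve is at 99% of its own peak and the fed curve at 89% of its own. Position on the curve contributes 0.99 / 0.89 = 1.11. The lower fed peak contributes 1 / 0.62 = 1.6. Most of the gap is therefore the lower Cmax.

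**7. Sensitivity of the fasted/fed ratio.**

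| Variant | 45 min | 55 min |
|---|---|---|
| Half-life 1.8 h | 1.80 | 1.62 |
| Half-life 1.6 h | 1.86 | 1.67 |
| 1.8 h, fed Cmax set to exactly 0.60 | 1.85 | 1.68 |
| 1.8 h, assumed fed absorption lag of 10 to 30 min | 1.76 to 1.98 | 1.47 to 1.55 |
| Assumed residual drug from two earlier doses, 4 to 8 h apart | 1.53 to 1.81 | 1.43 to 1.64 |
| Assumed half-size food effect (Tmax 58 min, AUC −10%), 1.8 h | 1.28 | 1.21 |

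At an illustrative 75 minutes, when the later tests might run, the fed level is 0.70 to 0.72 of the fasted level, a ratio of about 1.4.

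**8. Which scores are affected.** Meal state can change drug level only when the patient is on drug: Day 0 and the two visits of the amifampridine period. With both periods observed, Day 0 drops out of the treatment contrast:

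(HFMSE_A − HFMSE_0) − (HFMSE_P − HFMSE_0) = HFMSE_A − HFMSE_P

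For the treatment contrast the exposure is therefore the two active visits per patient. Day 0 error does stay in the randomization gate, which compares Day 0 on drug with the start of Run-in before drug.

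**9. Same-dose rule.** Sections 12.3.2 and 12.4 are near-identical on arranging visits around a dose. Only 12.3.2 requires the same dose each time.

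**The case against.** The case for leaving this alone has real content.

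- **The food contrast is extreme.** It is fasting against a high-fat breakfast, single dose, in healthy volunteers. Patients here take 3 or 4 doses a day and eat ordinary meals. This stands. A reader might infer that drug level routinely varies two-fold between visits, or that the Tmax shift alone produces this. Steps 6 and 7 support neither.
- **Free diet looks like a deliberate choice.** The protocol reports the food effect, and also that several adverse events, including nausea and dizziness, were more common when fasted. This is fair, but it argues against requiring a fasted state. It does not argue against consistency within a patient, or against recording the meal.
- **Habits may already be stable.** Doses are titrated individually during a run-in with the same free diet, so a patient with fixed habits is tested much as titrated. For that patient the change alters nothing. It helps only patients whose meal state varies.
- **There is no directional bias.** Sequence is randomized and blinded, and nothing suggests that meals differ by treatment. A reader might infer that the effect is diluted by a calculable percentage. That would need a concentration-effect relation, a proportion of fed visits and an all-fasted reference, none of which the documents give.
- **The same-dose omission may be only drafting.** The phrase in 12.3.2 could be meant for the whole study, and 9.3.3 already asks for dosing at about the same time each day. Even so, a site working from 12.4 will not see the rule. A reader might also infer that testing after a later dose weakens the measured effect. Nothing supports that: in the model, residual drug raises the level. The point is limited to added variability.

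**Conclusion.** The point holds as avoidable within-patient variability. The protocol standardizes the clock but not a factor that its own data show changes drug level at that clock. For the fasting versus high-fat extreme, the modelled fasted/fed ratio is about 1.6 to 1.9 at 45 to 55 minutes, without lag or residual drug. It falls to about 1.4 to 1.8 with assumed residual drug, and to about 1.2 to 1.3 with an assumed half-size food effect.

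These figures rest on mean values in healthy volunteers and a one-compartment model. They describe drug level, not motor function, and the documents do not allow conversion to HFMSE points. The noise affects the active-period scores and the Day 0 score used for randomization, and only where a patient's meal state actually changes. The absence of the same-dose sentence from 12.3.1 and 12.4 is a separate, plain inconsistency. Together they justify a low-cost improvement. They do not show that the trial's result would be biased.

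**What to change.** - Reconcile Protocol 7.4.1, 9.3.3 and 9.5.1 by asking each patient to keep the same meal state before the in-clinic dose on Days 0, 7, 14, 21 and 28. Which state is left to the sponsor.
- Record the time of the last meal before the in-clinic dose on the CRF, and add it to Table 1 and SAP Appendix 1.
- Repeat the same-dose sentence from 12.3.2 in 12.3.1 and 12.4, so that it covers Day 0 and both periods.

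The cost is one instruction, one CRF field and one repeated sentence. The downside is that patients keep one meal habit on five visit days. The change removes variation between visits. It does not alter exposure in a patient who already eats consistently.

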9.5.2 Contraception

Sexually active males and females of childbearing potential and their partners must use effective forms of contraception, such as condom for males or occlusive cap (diaphragm or cervical/vault caps) for females, during the study.

9.6 Safety Variables

Safety in this study will be determined from evaluation of AEs/SAEs, vital signs, clinical laboratory test results, ECGs, including QTc evaluation, and physical examination findings. Pregnancy testing is also required for females of childbearing potential. The timing of the required evaluations is described in the Schedule of Events in Table 1 and in Section 12 STUDY Procedures.

9.6.1 Adverse Events

The determination, evaluation and reporting of AEs will be performed as outlined in Section 10.

9.6.2 Vital Signs

Specific visits for obtaining vital signs are provided in Table 1 and in Section 12 STUDY Procedures. Vital signs will be measured while in a sitting position, after resting for 5 minutes, and include systolic blood pressure (SBP), diastolic blood pressure (DBP) measured in millimeters of mercury (mmHg), heart rate in beats per minute, respiration rate in breaths per minute. Body weight (kg) and temperature in °C will also be measured. Clinically significant changes from baseline will be recorded as AEs.

9.6.3 Clinical Laboratory Assessments

Specific visits for obtaining clinical laboratory assessment samples are provided in Table 1 Schedule of Events for the tests required by Protocol. The scheduled clinical laboratory tests are listed in Table 4. All abnormal clinical laboratory test result pages should be initialed and dated by an Investigator, along with a comment for each abnormal result indicating whether or not it is clinically significant. Any abnormal test results determined to be clinically significant by the Investigator should be repeated (at the Investigator's discretion) until the cause of the abnormality is determined, the value returns to baseline or to within normal limits, or the Investigator determines that the abnormal value is no longer clinically significant.

Each clinically significant laboratory result should be recorded as an AE. The diagnosis, if known, associated with abnormalities in clinical laboratory tests that are considered clinically significant by the Investigator will be recorded on the AE CRF.

Table 4 Clinical Laboratory Tests

Blood Chemistry	Hematology	Urine Tests	Other
Albumin	Hemoglobin	Appearance	Pregnancy test, if applicable
Alkaline phosphatase	Hematocrit	Color	
ALT (SGPT)	WBC count	pН	
AST (SGOT)	RBC count	Specific gravity	
Direct bilirubin	Platelet count	Ketones	
Total bilirubin	Differential cell count	Protein	
BUN		Glucose	
Calcium		Bilirubin	
Chloride		Nitrite	
Total cholesterol		Urobilinogen	
CO ₂ or bicarbonate		Blood in urine	
Creatine phosphokinase			
Creatinine			
Glucose			
GGT			
LDH			
Phosphorus			
Potassium			
Total protein			
Sodium			
Uric acid			

ALT, alanine aminotransferase; AST, aspartate aminotransferase; BUN, blood urea nitrogen; CO₂, carbon dioxide; GGT, gamma-glutamyltransferase; LDH, lactate dehydrogenase; RBC, red blood cell; SGOT, serum glutamic-oxaloacetic transaminase; SGPT, serum glutamic-pyruvic transaminase; WBC, white blood cell.

